Analytic Plans Primary endpoints are change in HbA_{1c} and DSMP-SR total score (treatment adherence) over 1 year. Secondary endpoints are: # of severe hypoglycemic events (Hypoglycemia Diary); measures of glycemic variability at each visit; and questionnaires obtained quarterly. The Full Analysis Set will include those who provide data at ≥ 1 follow-up visit. The Completer Analysis set will include those who provide data at all follow-ups. Efficacy analyses will be done on both sets.³¹³⁻³¹⁵ We will use multiple imputation for treatment of missing data.³¹³⁻³¹⁵ Obtained data will be summarized in graphs and tables. Categorical variables will be summarized by frequencies and percentages; continuous variables by mean, median, standard deviation (or SEM), minimum and maximum. Data will be summarized by primary group (UC and TC), secondary group (TC-TH, TC-IP, TC-IP/TH, TC-TH/CH) and measurement points.^{316,317} Model assumptions will be checked before analyses, and appropriate transformations or non-parametric methods will be used when indicated. For summarization of normally distributed data, group means and SEM will be presented. In case of substantial deviation from normality, boxplots will be presented. Exploratory subgroup analyses (e.g. race, ethnicity, gender, SES, secondary group) will be conducted as needed.^{318,319} Most tests will be performed against a two-sided alternative at the $\alpha = 0.05$ significance level and a 95% confidence interval and/or a p-value will be provided for inferential purposes. Data from both clinics will be pooled for analyses.^{316,317} All analyses will be done using the most recent version of SAS, SPSS, R or M-Plus.³¹⁵⁻³²² Demographic variables (age, gender, race, ethnicity, family structure, marital status, SES) and baseline values of primary and secondary end points, and questionnaire results will be summarized by group. If the normality assumption holds, t-tests of continuous baseline variables and Fisher exact test/chi-square test/CMH test for categorical variables will be used to compare the TC and UC groups at baseline; one-way ANOVA will be used for comparisons of secondary groups. The statistician will select analytic methods based on data distributions and any imbalanced baseline scores.³²³ Linear mixed effects modeling (continuous outcomes) or generalized linear mixed modeling (categorical outcomes) is planned for the hypotheses below.³¹⁵⁻³²² Treatment group (UC vs TC) and demographic characteristics will be fixed effects in these models, while site, physician, and within-subject effects will be random effects. The same analyses will be attempted for secondary groups, sample size permitting. We will use Holmbeck's methods³²⁴ to evaluate baseline demographic variables and questionnaire scores as moderators of TC-UC effects on primary outcomes and to evaluate mediation of effects on primary endpoints. Candidate mediators are variables that are obtained serially concurrent with the primary endpoints at ≥ 3 visits.

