
Sample Size and Statistical Power: Recruitment ended at the end of March 2020. A total of 115 families were recruited. Allowing for some attrition prior to randomization, a sample of 100 patients (65 TC and 35 UC) yields 87.4% power to detect a clinically meaningful group differences in mean HbA_{1c} of 0.5% (~0.7 SD) versus the alternative of equal means using a t test with $p = .05$. Limiting recruitment to those with HbA_{1c} = 7.5-10.0% is anticipated to reduce the SD from 1.5% for the general adolescent T1D population to 0.7%, boosting effective statistical power for the RCT. The predicted 12-month means are 8.1% (TC) and 8.6% (UC). If the SD is 1.0%, our power is reduced to 71.3%; if it is 1.5% as in the general population, our power is 50.9%. This sample size also achieves power of 78.2% to detect a clinically meaningful mean differences in the DSMP-SR

total score of 7.0 points (~0.6 SD) at 1 year. The estimated mean values are 63.0 (TC) and 56.0 (UC). This preliminary trial will yield rich data that could be used to guide the sampling plan for a future, more ambitious, multi-center trial.³²⁵⁻³²⁷ The following hypotheses will be tested:

Hypothesis 1: Compared with UC patients, those randomized to TC will have significantly more favorable primary (HbA_{1c} and DSMP-SR scores) and secondary (frequency of severe hypoglycemia and level of glycemic variability) diabetes management outcomes at their 6, 9, and 12 month follow-up visits.

Hypothesis 2: Compared with UC patients, those randomized to TC will demonstrate more favorable scores on the T1DAL, PAID, and CPI at follow-up measurements.

Hypothesis 3: Significantly higher scores will be obtained on the DCI completed by HCPs describing TC care compared to HCPs describing UC care.

Hypothesis 4: Effects of TC on HbA_{1c} and DSMP-SR scores will be moderated by demographic variables (youth age, family SES, # of adult caregivers in the home) and by baseline scores on the T1DAL, PAID, and CPI. More benefit from TC will accrue to youth who are younger, from two-parent families with higher SES, and with more favorable scores on the T1DAL, PAID and CPI.

Hypothesis 5: Effects of TC on HbA_{1c} and DSMP-SR scores will be mediated by changes in scores on the T1DAL, PAID, and CPI. More benefit from TC will accrue to youth with favorable changes in T1DAL, PAID and CPI scores during the 12 months of the study.

[figure not shown]

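### Hypothesis 1 claims benefit on the primary outcomes at months 6, 9 and 12, while the endpoints and power concern one year, and the plan names no deciding contrast; DSMP-SR is not collected at month 9

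*Combined protocol and SAP*

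**What the plan says.** All of this is in section 3.4 (Approach) of the combined protocol and SAP.

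- **Endpoints.** Analytic Plans: "Primary endpoints are change in HbA_{1c} and DSMP-SR total score (treatment adherence) over 1 year". The Measurement Schedule text says the same.
- **Power.** Sample Size and Statistical Power: "a sample of 100 patients (65 TC and 35 UC) yields 87.4% power" for a 0.5% HbA1c difference by t test. The predicted 12-month means are 8.1% (TC) and 8.6% (UC), with an anticipated SD of 0.7%. Stated power falls to 71.3% at SD 1.0% and 50.9% at SD 1.5%. For DSMP-SR it is 78.2% for 7.0 points (about 0.6 SD) at 1 year.
- **Hypothesis 1.** TC will be significantly better than UC on primary and secondary "diabetes management outcomes at their 6, 9, and 12 month follow-up visits". HbA1c and DSMP-SR are both listed there as primary.
- **Model.** Linear mixed models are planned for the continuous outcomes. The listed fixed effects are treatment group and demographics; site, physician and within-subject effects are random. No visit or treatment-by-visit term is listed.
- **Schedule.** Table 3 has HbA1c at 0, 3, 6, 9 and 12 months and DSMP-SR at 0, 6 and 12. The accompanying text limits questionnaires to those three visits. The Analytic Plans, in listing secondary endpoints, describe questionnaires as quarterly, which conflicts with both.

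No section says whether month 12, any visit, all visits or a pooled effect decides Hypothesis 1, and no error control across visits is given.

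**The concern.** The endpoint definition and the power calculation point to one comparison at one year. The hypothesis that these serve lists three visits. HbA1c is measured at all three, so every contrast can be run, and the text does not settle in advance which one counts.

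The choice can change the conclusion on the same data. A benefit at month 6 that has gone by month 12 supports Hypothesis 1 if any visit suffices, but not if month 12 decides. A benefit that builds up and is clear only at month 12 meets the endpoint as powered, but fails if all three visits must be significant. For DSMP-SR, one of the three named tests has no scheduled data behind it.

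**Working it through.** **Inputs from the plan.** 65 TC and 35 UC; HbA1c difference 0.5%; SD 0.7% (alternatives 1.0% and 1.5%); t test at .05, taken as two-sided.

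**Assumptions not in the documents.** Equal between-visit correlation r from 0.5 to 0.9, and the effect profiles over time given below.

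**1. The plan's own power.** Noncentrality = (difference/SD) × √(65 × 35/100) = (difference/SD) × 4.770, with 98 df and critical value 1.984.

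- SD 0.7: 0.714 × 4.770 = 3.407, power 92.1% (stated 87.4%).
- SD 1.0: 0.5 × 4.770 = 2.385, power 65.6% (stated 71.3%).
- SD 1.5: 0.333 × 4.770 = 1.590, power 35.0% (stated 50.9%).
- DSMP-SR at 0.6 SD: 2.862, power 80.9% (stated 78.2%). An effect of about 0.58 SD gives 78.2%, so rounding may explain this one.

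The HbA1c figures do not reproduce, and they miss in different directions. Losing 15% of patients would give 87.4% at SD 0.7, but no single variant tried (sidedness, alpha, split, total size) fits all three. The comparisons below therefore use the recomputed 92.1% and 65.6%.

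**2. Readings of Hypothesis 1 for HbA1c.** Three correlated test statistics were simulated, each compared with 1.984. Power is at SD 0.7.

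| r | Any visit: false positives | All visits: power, constant 0.5% | All visits: power, build-up 0.25, 0.375, 0.5% |
|---|---|---|---|
| 0.5 | 12.6% | 83% | 34% |
| 0.7 | 10.9% | 85% | 37% |
| 0.8 | 9.9% | 86% | 38% |
| 0.9 | 8.4% | 88% | 39% |

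With independent visits the any-visit rate would be 1 − 0.95³ = 14.3%. These rates count a significant difference in either direction. In TC's favour alone they are about 4-6%, against a nominal 2.5%. The all-visits rule cannot exceed 5%.

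At SD 1.0 the all-visits power is 41-51% for a constant effect (r 0.5 to 0.8) and 14-21% for the build-up (r 0.5 to 0.9), against 66% for month 12 alone.

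**3. One pooled effect.** As a proxy, take the simple mean of the three visits. Its SD is SD × √((1 + 2r)/3).

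- Constant 0.5%, SD 0.7: at r = 0.5 the noncentrality is 3.407/0.816 = 4.17, power about 99%; at r = 0.9 it is 3.407/0.966 = 3.53, power about 94%.
- Build-up (mean effect 0.375%): noncentrality 3.13 at r = 0.5 and 2.64 at r = 0.9, power about 87% and 75%.

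**4. A fading effect (assumed 0.5, 0.25, 0%), SD 0.7.** The any-visit rule declares success about 92-93% of the time. Month 12 alone does so in TC's favour about 2.5% of the time, because the true month-12 difference is zero.

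**5. DSMP-SR.** Hypothesis 1 names months 6, 9 and 12; the schedule has months 0, 6 and 12. The month-9 test has no data.

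**The case against.** The strongest reply is that the planned mixed model already settles the matter. As listed, with treatment group and no visit terms, it yields one TC-UC coefficient per outcome, hence one test and no inflation across visits. Step 3 shows good power for it at SD 0.7. A one-year change endpoint can also be read as a repeated-measures analysis. This stands as far as it goes: three separate contrasts are not inevitable. But the plan does not name the pooled coefficient as decisive. It is also a different quantity from the 12-month difference that was powered and from the visit-by-visit claim in Hypothesis 1.

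A reader might infer that the plan must either double its error rate or lose its stated power. The documents do not support that, for four reasons:

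- A pooled test, or a month-12 contrast named in advance, avoids both.
- Hypothesis 1 joins the visits with 'and', which reads more naturally as all visits, and that reading does not inflate error. A doubling needs the any-visit reading and a correlation of about 0.8 or lower.
- The all-visits loss is modest at SD 0.7 if the effect is constant: 83-88% lies close to the stated 87.4%. The large losses depend on an assumed build-up.
- The stated 87.4% does not reproduce, so it is a weak yardstick for lost power.

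The protocol also calls this a preliminary trial and sets no formal pass/fail rule. That lowers the stakes, but Hypothesis 1 still claims significance.

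One could cite the quarterly questionnaires in the Analytic Plans as support for a month-9 DSMP-SR. Table 3 and the explicit limit in the text beside it say otherwise.

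**Conclusion.** The point holds as an unresolved inconsistency that should be corrected. The endpoints and power concern one year, Hypothesis 1 names three visits, no deciding contrast is given, and the month-9 DSMP-SR test cannot be done under the schedule. These facts come from the text alone.

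The size depends on the reading. For HbA1c, with correlation 0.5 to 0.9, false positives are 1.7 to 2.5 times nominal under any-visit. All-visits costs about 4 to 9 points of power at SD 0.7 if the effect is constant, and more than 50 points if it builds up linearly. A build-up is plausible for care delivered over about four visits in 12 months, but the documents give neither a time profile nor a correlation. No corresponding figures were computed for DSMP-SR. Whether two primary endpoints need an error-control rule between them is a separate question.

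**What to change.** - Reword Hypothesis 1 so that the deciding test for each primary endpoint is the TC-UC contrast in change from baseline to month 12, from the planned mixed model with visit and treatment-by-visit terms added.
- Report HbA1c at months 6 and 9, and DSMP-SR at month 6, as supportive estimates with 95% confidence intervals that cannot by themselves meet Hypothesis 1.
- Delete month 9 for DSMP-SR, and align the reference to quarterly questionnaires with Table 3.
- Recompute the HbA1c power for this contrast. The current text uses the SD of HbA1c, not of its change, and its figures do not reproduce.

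This takes a few sentences and one recalculation, with no new data. It should be dated before the groups are compared. The cost is that an early benefit that fades by month 12 can no longer be declared as meeting Hypothesis 1.

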Experimental Design: Two TC teams (APN, RD and Psy. Fellow) will be constituted and trained, one each at NCH and AIDHC. A backup for each team member will also be identified and trained. Families will be randomized by [name] staff to TC-IP (n=50), TC-TH (n=50) or UC (n=50), using a prepared randomization list, stratified by insulin modality (pump or injections) and HbA_{1c} (\leq or $>$ 8.7%). We rejected randomization by sites due to logistical obstacles and since site differences might obscure detection of treatment effects. Randomization at the level of families reduces those concerns but introduces contamination issues as TC elements could intrude into UC visits. Efforts to counter this potential confound are described below. Each youth/parent will receive the assigned care (TC or UC) for approximately 4 successive follow-up visits across approximately 12 months. This period is adequate to detect clinically meaningful changes in HbA_{1c} and adherence. The design also permits exploratory analyses of modality of care (Face-to-Face vs. Telehealth), gender, race and ethnicity as moderators of treatment outcomes.

Treatment Conditions: The original RCT design is shown above. Treatment conditions include Usual Care and Transdisciplinary Care delivered in person or through telehealth. Elements of TC care are employed with some adolescents with T1D at AIDHC (i.e., APN and Psychologist see some patients together); this is much less true at NCH. AIDHC patients who have had such a visit within 12 months are ineligible for this study.

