The Readiness Assessment for Emerging Adults Diagnosed with Diabetes in Youth (READDY): The READDY is a 13 item self-assessment of adolescents' readiness to transfer from pediatric to adult care for T1D. The scale has been validated by researchers at Cincinnati Children's Hospital and Children's Hospital of Seattle and a publication reporting these findings is under editorial review at this time.

Diabetes Care Inventory (DCI): This 17 item scale was developed by the research team to assess the nature of diabetes care provided to each participant in the study and to gauge the extent to which elements of Transdisciplinary Care are being provided to participants. Completed by healthcare providers, the measure includes questions regarding the provider's approach to care (i.e., use of motivational interviewing), the extent of their collaboration with providers outside of their discipline, the nature of their communication with other providers, and the format of care visits (e.g., multiple providers in the room at the same time). Aspects of the measure are based upon a provider-completed measure of use of motivational interviewing techniques.³¹² The DCI will be completed by all endocrinologists, nurse practitioners, dietitians, social workers, and psychologists seeing the patient during the course of the study (identified through the patient's EHR) after the final study visit for each enrolled adolescent.

Post-RCT Qualitative Interviews: These interviews (See Appendix) will obtain parent/adolescent views of the TC process, factors affecting its efficacy, advantages/disadvantages of the model, and suggested refinements. Qualitative interviews of representatives of third party payers will seek their views of the viability of the TC model, based on the RCT results and costs relative to UC. Audio recordings of interviews will be transcribed verbatim and coded by trained coders under the supervision of [name].

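### The Hypothesis 3 model names no random effect for the provider who completes the DCI, so clustering by rater is left out if *physician* is read literally

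*Combined protocol and SAP*

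**What the plan says.** All references are to section 3.4 of the combined protocol and SAP.

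- **Hypothesis 3** (after Sample Size and Statistical Power): "Significantly higher scores will be obtained on the DCI completed by HCPs describing TC care compared to HCPs describing UC care".
- **Analytic Plans**: "Linear mixed effects modeling (continuous outcomes) or generalized linear mixed modeling (categorical outcomes) is planned for the hypotheses below". Treatment group and demographics are fixed effects, "while site, physician, and within-subject effects will be random effects". On the error rate: "Most tests will be performed against a two-sided alternative at the $\alpha = 0.05$ significance level".
- **Diabetes Care Inventory (DCI)**: "The DCI will be completed by all endocrinologists, nurse practitioners, dietitians, social workers, and psychologists seeing the patient during the course of the study", and this happens "after the final study visit for each enrolled adolescent". The unit of data is therefore one form per provider per patient. The items cover the provider's own approach to care, collaboration, communication and visit format.
- **Experimental Design**: "Two TC teams (APN, RD and Psy. Fellow) will be constituted and trained, one each at NCH and AIDHC". Also: "A backup for each team member will also be identified and trained".
- **Prevention of TC-UC Contamination**: UC patients stay with the providers they already have, and those who need psychological services are sent to psychologists outside the TC teams.

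No sample size, power, SD or ICC is given for the DCI.

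**The concern.** Several DCI items describe habits of the person answering, such as use of motivational interviewing. One clinician's forms can therefore be expected to resemble each other across patients. In TC a handful of clinicians supply most of the forms, and those clinicians hardly appear in UC. A patient-level effect cannot remove that similarity, because it runs across patients. A site effect cannot remove it either, because both arms share each site. A physician effect would miss the nurse, the dietitian and the psychology fellow.

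If rater variation is left out, the standard error of the TC-UC difference is too small. The DCI is one of the planned means of showing that TC was delivered and that UC was not contaminated, and Limitations presents the contamination evaluation as important for a later application. Separation between the arms could look firmer than a few clinicians' forms can support, which would colour the reading of any HbA1c result.

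**Working it through.** **Plan's own figure.** There is none to reproduce for the DCI beyond the nominal two-sided 0.05.

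**Inputs from the documents.** 65 TC and 35 UC patients (Sample Size and Statistical Power); 2 teams of 3 = 6 core TC clinicians, up to 12 with backups (Experimental Design).

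**Assumptions not in the documents.** Two forms per UC patient (70 forms); 12 UC raters; patient ICC 0.10 in the simulations; rater ICC 0.05 to 0.30.

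**Step 1: concentration of TC forms.** 65 × 3 = 195 team forms; 195 / 6 = 32.5 per clinician. If one endocrinologist also rates each TC patient, there are 65 × 4 = 260 forms, and the team supplies 195 / 260 = 75%. If backups share equally, 195 / 12 = 16.25 per clinician.

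**Step 2: design effect in TC**, 1 + (m − 1) × ICC, where m is forms per clinician.

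| Rater ICC | 6 raters: 1 + 31.5 × ICC | 12 raters: 1 + 15.25 × ICC |
|---|---|---|
| 0.05 | 2.6 | 1.8 |
| 0.10 | 4.2 | 2.5 |
| 0.30 | 10.5 | 5.6 |

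**Step 3: hand check of the error rate.** This ignores patient clustering and takes equal forms per rater and total variance 1. With k TC raters, the true variance of the difference is ICC/k + (1 − ICC)/195 + ICC/12 + (1 − ICC)/70. A test that ignores rater uses 1/195 + 1/70 = 0.0194.

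- k = 6, ICC 0.05: true variance 0.0309; ratio 1.59; effective critical value 1.96/√1.59 = 1.55; error 12%.
- k = 6, ICC 0.10: 0.0425; ratio 2.19; 1.96/√2.19 = 1.32; error 19%.
- k = 6, ICC 0.30: 0.0886; ratio 4.56; 1.96/√4.56 = 0.92; error 36%.
- k = 12, same ICCs: ratios 1.38, 1.76 and 3.28; errors about 10%, 14% and 28%.

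**Step 4: simulation under the null.** About 400 runs per setting for the mixed models, so the Monte Carlo standard error is about 1 point near 5% and 2.4 points near 38%. There were 3,000 runs for the t test on patient means.

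| Analysis | TC raters | ICC 0.05 | 0.10 | 0.30 |
|---|---|---|---|---|
| Mixed model, patient + attending physician | team only | 11% | 22% | 38% |
| Same | team + endocrinologist | 8% | 12% | 29% |
| t test on patient means | team only | 14% | 21% | 38% |
| Same | team + endocrinologist | 12% | 15% | 31% |
| Mixed model, patient + completing provider, normal reference | team only | 5% | 6% | 7% |
| Same | team + endocrinologist | 4% | 4% | 6% |

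At rater ICC zero the patient-mean t test rejects 5 to 7% of the time, so the excess in the table is mostly due to raters. With a fixed t reference on 6 df, the completing-provider model rejects at most 4% of the time, which is conservative. The simulated models had no site term. A site intercept is common to both arms and drops out of the within-site comparison, so it would not supply the missing rater variance.

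**The case against.** The best defence is that the plan already uses mixed models for its hypotheses and already names a clinician-level effect. A reader might infer that DCI forms are to be analysed as independent observations; Analytic Plans rules that out. If *physician* is understood as whichever provider filled in the form, the error is about 4 to 7% and nothing is wrong. There is some room for that reading, since an advanced practice nurse may be the main diabetes provider (Table 2; Usual Care). Against it, the Participants section uses HCP as the inclusive term, covering MDs, nurses, dietitians, social workers and psychologists. Table 2 and the Transdisciplinary Care paragraph use *physician* for the MD or endocrinologist. The literal reading is the more natural one, and the plan does not settle the matter.

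A reader might also infer that six people supply nearly all TC forms. The documents do not establish that: endocrinologists and social workers who saw the patient also rate, and backups are trained. *Most* is supportable.

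Two further points stand in part. First, the teams' behaviour is the intervention in this trial, and some items, such as visit format, differ by design, so a no-difference null has limited practical weight. The interval around the difference still matters. Second, the DCI is not the only fidelity evidence: a parent checklist and record review of UC visits are also planned.

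**Conclusion.** The point holds in limited form. The random-effects rule in Analytic Plans, followed literally for Hypothesis 3, omits clustering by the provider who completes the form, and rater is largely nested in arm. The resulting type I error is roughly 8 to 14% at a rater ICC of 0.05 and 29 to 38% at 0.30. The lower figures apply when an endocrinologist also rates each TC patient; full, equal sharing with backups also lowers the error (about 10% and 28% by the hand check).

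These sizes rest on an assumed ICC, an assumed number of UC raters and forms, and the literal reading of *physician*. It would be tempting to conclude that the error rate is known to be far above 5%. The documents give no ICC, so that cannot be stated as fact. The consequence is confined to a check of care delivery and contamination; the primary endpoints are not affected.

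**What to change.** In Analytic Plans, state for Hypothesis 3 that the physician effect is replaced by a random intercept for the provider who completes the DCI, of any discipline, crossed with a random intercept for patient. Use Kenward-Roger or Satterthwaite degrees of freedom. These were not simulated here, but with so few TC raters a normal reference is hard to defend. Report the TC-UC difference with its confidence interval and the number of raters per arm, so that readers can see how few clinicians carry the TC result.

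Comparing rater-level means is not a safe substitute, because endocrinologists may rate patients in both arms. In the simulated layout with endocrinologist raters, a Welch test on rater means rejected only 3% of the time at ICC 0.05 and under 1% at 0.30.

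The cost is small: one line of specification and a rater identifier on each form. Providers are already to be identified through the patient's electronic record, but the form itself is not in the document, so confirm that it records who completed it. The statistical price is a wider confidence interval.
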